6.2 Evaluation of Pharmacokinetic Parameters

Non-compartmental analysis will be used for estimation of pharmacokinetic parameters.

The following pharmacokinetic parameters will be calculated for atovaquone (ATV), proguanil (PG), cyloguanil (CG), amodiaquine (AQ) and desethyl-amodiaquine (DEAQ):

C_{max}	Maximal observed plasma concentration 
 For multiple peaks, the highest post-dose concentration will be reported as C_{max}
t_{max}	Time at which the maximum plasma concentration occurs 
 In case that multiple peaks are of equal magnitude, the earliest T_{max} will be reported
AUC_{0-t}	Area under the plasma concentration curve from time zero up to the last quantifiable concentration

AUC _{0-inf}	Area under the plasma concentration-time curve from time zero extrapolated to infinity
λ_z	Terminal elimination rate constant
$t_{1/2}$	Terminal elimination half-life 
 • Calculated as $\ln(2)/\lambda_z$

For individual plasma concentration data, the actual time of ATV-PG and AQ administration and actual blood sampling time will be used in the derivation of the PK parameters. If there is any doubt in the actual time a sample was taken, then the scheduled time will be used.

AUC values will be calculated using the linear/log trapezoidal method, applying the linear trapezoidal rule up to C_{max} and the log trapezoidal rule for the remainder of the curve. Samples below limit of quantification (LOQ) prior to the first quantifiable concentration will be set to zero. Samples with concentrations below LOQ after the first quantifiable concentration will be set to 'missing' and omitted from the analysis. Other pharmacokinetic parameters will be calculated according to standard equations.

PK parameters will be listed for each individual subject and summarized by treatment group. Descriptive statistics for PK parameters will include number of observations (n), arithmetic mean (Mean), standard deviation (SD), arithmetic coefficient of variation (%CV), geometric mean, geometric %CV, median, minimum and maximum.

If a value is considered to be anomalous due to being inconsistent with the expected PK profile, it may be appropriate to exclude this point from the PK analysis. However, the exclusion of data must have strong justification and will be documented in the raw data and in the clinical study report. The following conditions for PK parameter inclusion may also be applied:

- AUC, λ_z and $t_{1/2}$ to be excluded if the regression does not include at least 3 different time points in the terminal phase (after C_{max} , but excluding the concentration at T_{max})
- $T_{1/2}$, λ_z to be excluded if the coefficient of determination, Adj_Rsq in the regression is less than 0.80
- AUC_{0-inf} is excluded if the %extrapolated is greater than 20%

Additional PK parameters may be calculated, as appropriate.

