Following a single administration of *Malarone* to healthy subjects, the median T_{max} (range) of ATV, PG and CG respectively was 3.25 (1.75-5.25) hours, 4.25 (3.00-5.50) hours, and 5.25 (4.50-8.25) hours. The median elimination half-life of ATV, PG and CG respectively was 87.2 (37.2-116) hours, 8.03 (4.28-29.5) hours and 10.2 (6.42-17.3) hours [12]. Concomitant treatment with tetracycline, metoclopramide, rifampin/rifampicin and rifabutin is known to reduce ATV plasma concentration [6].

Administration of *Malarone* with dietary fat increases the ATV AUC 2 to 3 times and C_{max} 5 times over fasting; the absolute bioavailability of atovaquone when taken with food was 23%. *Malarone* Tablets should be taken with food or a milky drink [6].

Potential for pharmacokinetic interaction between ATV and PG and between ATV-PG and AQ

There is no overlap in the clearance mechanisms and inhibition profiles of the components and metabolites of the two products which indicates a low potential for pharmacokinetic interaction between ATV-PG and AQ based on *in vitro* data [13]. There was no pharmacokinetic interaction between ATV and PG at the recommended dose [6].

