g: Vital signs and 12-lead ECG to be carried out prior to any blood sampling (where time points coincide). Vital signs will be measured after rest of at least 5 minutes in supine position and in standing at screening only. From Cohort 2 onwards, standing blood pressure measurement will be performed at 2H and 5H post-dose (on study days 1, 2 and 3). In addition to these time-points, an unscheduled standing blood pressure measurement should also be performed if a subject wish to leave the bed between these time-points.

h: Continuous 12-lead telemetry will be recorded from at least 1-hour pre-dose to 24 hours post-dose on Day 1 and Day 3.

i: At screening Holter will be performed to exclude pre-existing ECG abnormalities.

j: Coagulation at screening and Day -1.

k: pre-dose. Samples will be analysed only if required as per the Adaptive Feature number 9.

Table 2. Detail schedule of assessments for in-house stay

Study Day	Time (h)	PK blood sampling	Meals	12-lead ECG ^a	Vitals ^b	
D1	-3			X		
	-2.5			X		
	-2			X		
	-35 minutes	X			X	
	-30 minutes		X ^c			
	0					
	1	X			X	
	2	X			X ^e	
	3	X				
	4	X				
	5	X		X ^c	X	X ^e
	6	X			X	
D2	8	X		X	X	
	10		X			
	12	X		X		
	-35 minutes	X		X	X	
	-30 minutes		X ^c			
D3	0					
	2				X ^e	
	5				X ^e	
	-3			X		
	-2.5			X		
	-2			X		
	-35 minutes	X			X	
	-30 minutes		X ^c			
	0					
	1	X			X	
	2	X			X	X ^e
	D4	3	X		X	
4		X		X		
5		X		X	X ^e	
6		X		X		
8		X		X	X	
10			X			
12		X		X		
24		X	X ^d	X	X	

a: 12-lead ECG will be measured in triplicate after a rest period of at least 10 min.

b: Vital signs will be measured after rest of at least 5 min in supine position.

-
- c: Breakfast is the first meal and will be given at 30 minutes pre-dose. The 5-hour procedures are to be completed prior to lunch being given.
 - d: Optional breakfast after clinical assessments.
 - e: Standing blood pressure measurement will also be performed.

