2.2 Endpoints

Primary

- Safety and tolerability as measured by the incidence of treatment-emergent adverse events (TEAEs) including the clinical signs, nausea, vomiting and diarrhoea, proportion of subjects with clinically relevant changes in laboratory safety tests (haematology, chemistry (in particular ALT, AST and bilirubin increases) and urinalysis), proportion of subjects with morphological and/or rhythm abnormalities on electrocardiogram (ECG), proportion of subjects with clinically significant changes in ECG time intervals (PR, QRS, QT and QTc intervals) and proportion of subjects with clinically significant changes in vital signs (systolic blood pressure, diastolic blood pressure and pulse rate).

Secondary

- PK parameters derived by non-compartmental methods including maximum observed plasma concentration (C_{max}), time to maximum plasma concentration (t_{max}), area under the plasma concentration-time curve from time zero to last detectable plasma concentration (AUC_{0-t}), area under the plasma concentration-time curve from time zero extrapolated to infinity (AUC_{0-inf}), terminal elimination rate constant (λ_z), terminal elimination half-life ($t_{1/2}$).
- Baseline corrected QTc (ΔQTc) as a function of the concentrations of AQ and DEAQ when administered alone, and when administered in combination with ATV-PG.

3. Trial Design

The study is a randomized, double-blind, placebo controlled, parallel group study to determine the tolerability and safety of ATV-PG + AQ, ATV-PG + AQ placebo, ATV-PG placebo + AQ, and ATV-PG placebo + AQ placebo administered once daily for 3 days to healthy adult male and female subjects.

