6.3 Statistical Analysis on PK Parameters

The PK parameters will be listed for each subject and summarized using descriptive statistics (N - the number of subjects, arithmetic mean, SD - standard deviation, CV - coefficient of variation, geometric mean, geometric CV, median, minimum, maximum).

It is noted that for reporting purposes, T_{max} will be described using Median (min, max), and all other parameters will be described using mean, geometric mean and CVs.

7. *Methods for Withdrawals, Missing Data and Outliers*

The individual plasma concentration data and the actual timing of study drug administration and blood sampling will be used throughout the analyses. If there is any doubt about the actual time at which a sample was taken, then the scheduled time will be used. For PK data analysis, please see Section 4.13.1 regarding the handling of missing and BLQ values.

If medication dates are incomplete and it is not clear whether the medication was concomitant, it will be assumed to be concomitant.

AEs with unknown start date/time will be assumed to be treatment-emergent unless the end date/time is known to be before the first administration of study drug. Otherwise missing or partial dates will be listed as such.

There will be no further imputation of missing data (i.e., subjects who prematurely discontinue from the study will not be included in summary statistics or analyses beyond the time of discontinuation).

Depending on the extent of missing values, the appropriateness of the methods described for handling missing data may be reassessed prior to database lock (to examine the sensitivity of results to handling of missing data).

References

- [1] Garnett, C., Bonate, P.L., Dang, Q. et al. Garnett C, Bonate PL, Dang Q, Ferber G, Huang D, Liu J, Mehrotra D, Riley S, Sager P, Tornoe C, Wang Y. Correction to: Scientific white paper on concentration-QTc modelling. *J Pharmacokinet Pharmacodyn.* 2018b; 45 (3): 399.

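### SAP 6.2 ties Cmax and tmax to no dose, so across three daily doses the median tmax of AQ and PG, and less so CG, can differ between arms by 24 to 48 h by chance

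*SAP*

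**What the plan says.** Treatment is "administered once daily for 3 days to healthy adult male and female subjects" (SAP 3, Trial Design). Protocol Table 2 schedules PK samples from 1 to 12 h after the Day 1 and Day 3 doses. Day 2 has only a sample 35 minutes before dosing, and Day 4 has a sample 24 h after the last dose.

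Both Cmax and tmax are named secondary endpoints (Protocol 2.2.2, SAP 2.2). SAP 6.2 defines tmax as "Time at which the maximum plasma concentration occurs". On Cmax it says "For multiple peaks, the highest post-dose concentration will be reported as" Cmax, and where peaks are equal the earliest time is taken. AUC0-t is the "Area under the plasma concentration curve from time zero up to the last quantifiable concentration", which is one interval with one time zero. SAP 6.3 states that tmax "will be described using Median (min, max), and all other parameters will be described using mean, geometric mean and CVs".

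Nothing in Protocol 10.5 or in SAP 4, 6.2 or 6.3 asks for Day 1 and Day 3 values separately, or says from which dose tmax is counted. The SAP does separate days elsewhere: the time factor in the QTc model of SAP 5.4.5 has a separate level for each timepoint on each day.

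**The concern.** With one Cmax and one tmax per analyte and two sampled dosing days, the literal derivation searches the whole record for the highest value and reports its time from the start. For an analyte that accumulates little over three days, the Day 1 and Day 3 peaks are of similar height. Ordinary day-to-day variation then helps decide which day supplies tmax, and the choice moves the value by 48 h.

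The PK objective is to determine the pharmacokinetics alone and in combination, so readers will set the arm medians side by side. A gap of one or two days could appear with no change in absorption. It would also be far larger than any plausible change in the time to peak after a dose.

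**Working it through.** The documents give no tmax calculation and no sample-size figure on this point, so there is nothing to reproduce.

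**Inputs from the documents**
- Doses at 0, 24 and 48 h.
- Half-lives (Protocol 1): AQ 7.9 h and DEAQ 211 h, both from patients. For single-dose ATV-PG in healthy subjects: "The median elimination half-life of ATV, PG and CG respectively was 87.2 (37.2-116) hours, 8.03 (4.28-29.5) hours and 10.2 (6.42-17.3) hours".
- Median tmax after a dose (Protocol 1): AQ 0.79 h, PG 4.25 h, CG 5.25 h (range 4.50 to 8.25 h).
- Arm sizes (SAP 3.1): 8 on the combination, 12 on each monotherapy.

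**Assumptions**
- One-compartment decline at the cited half-lives, with the same dose each day.
- Log-normal peaks with a within-subject, day-to-day CV of 10% to 50%. The documents give no value.
- Time to peak after a dose drawn with equal probability from sampled times of 1, 1, 1, 2 h (AQ), 3, 4, 4, 5 h (PG) and 5, 5, 6, 8 h (CG).

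**Step 1. Expected peak ratio, Day 3 to Day 1.** R = 1 + r + r², with r = 2^(−24/half-life).
- AQ: r = 0.122, R = 1.14
- PG: r = 0.126, R = 1.14
- CG: r = 0.196, R = 1.23
- ATV: R = 2.51
- DEAQ: R = 2.78

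**Step 2. Chance that the overall maximum falls on Day 3.** P = Φ(ln R / (√2·σ)), with σ² = ln(1 + CV²). For AQ at CV 20%, σ = 0.198 and P = Φ(0.128/0.280) = 0.68, so about 32% of subjects would have tmax on Day 1.

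| CV | 10% | 20% | 30% | 40% | 50% |
|---|---|---|---|---|---|
| AQ | 82% | 68% | 62% | 59% | 58% |
| PG | 83% | 68% | 63% | 60% | 58% |
| CG | 93% | 77% | 69% | 65% | 62% |

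For ATV and DEAQ the chance is 92% or more throughout.

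**Step 3. Difference in arm medians, 8 against 12, with no true difference** (40,000 simulated trials per case, time counted from the first dose).

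| CV | 10% | 20% | 30% | 40% | 50% |
|---|---|---|---|---|---|
| AQ, gap above 12 h | 5% | 34% | 49% | 55% | 59% |
| PG, gap above 12 h | 5% | 32% | 47% | 54% | 58% |
| CG, gap above 12 h | 0.1% | 11% | 29% | 41% | 48% |
| AQ, gap above 40 h | 1% | 11% | 18% | 22% | 24% |
| PG, gap above 40 h | 1% | 10% | 18% | 21% | 24% |
| CG, gap above 40 h | 0% | 2% | 9% | 14% | 18% |

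Most gaps above 12 h are therefore near 24 h, where one arm divides evenly between the days. If 6 of 12 AQ subjects peak at 1 h and 6 at 49 h, the median is (1 + 49)/2 = 25 h. That is on Day 2, when only a pre-dose sample is taken.

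**Step 4. Same simulation with tmax taken within one dosing day.** The gap between medians never exceeds 1 h (AQ), 2 h (PG) or 3 h (CG).

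**Sensitivity to half-life.** Over the protocol's ranges, R runs from 1.02 to 1.89 for PG and from 1.08 to 1.53 for CG. At CV 20%, the chance of a Day 3 maximum then runs from 53% to 99% for PG and from 61% to 94% for CG.

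**The case against.** **The whole-record rule is inferred.** The SAP never states it. The wording on multiple peaks could describe one post-dose profile, and SAP 6.2 uses actual administration times. If tmax were counted from the latest dose, the 48 h gap would vanish. This stands as a limit on the claim. It does not remove the defect: the single time zero for AUC fits the whole-record reading, and counting from the latest dose would still mix dose 1 with dose 3. Two programmers could follow SAP 6.2 and report different medians.

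**The size depends on an assumed CV.** This stands. At 10%, most maxima fall on Day 3 and the AQ, PG and CG medians split in 5% of null trials or fewer.

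**The comparison is descriptive and other outputs remain.** This also stands. No between-arm PK test is planned, and the study is exploratory. SAP 6 lists all concentrations, summarises them by time point and treatment, and plots individual and mean profiles, so timing on each day stays visible. SAP 6.2 permits additional parameters, but it does not require per-day values.

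**Stronger readings that the documents do not support.** A reader might infer that no AQ peak can occur near 25 h. Dose 2 is given at 24 h, so a peak can occur there and is merely unsampled. A reader might also treat tmax as the only endpoint that reflects absorption rate, but Cmax depends on rate as well as extent.

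**Conclusion.** The point holds as a defect of definition with a foreseeable numerical consequence. Applied literally, SAP 6.2 yields tmax values in Day 1 and Day 3 clusters for AQ and PG, and to a lesser degree for CG, whose clusters lie at about 5 to 8 h and 53 to 56 h. At an assumed CV of 20% to 40%, the AQ and PG medians would differ by more than 12 h in roughly a third to just over half of trials with no true difference. For CG the range is 11% to 41%. ATV and DEAQ are little affected.

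It would go too far to say that tmax is fixed largely by chance, or that arm medians cannot be compared at all. Both statements need a CV that the documents do not give, and both fail near 10%. The sizes also rest on point half-lives, simple decline and equal dosing on all days. The individual stopping rules in Protocol 4.4 allow dosing to end before Day 3. A subject stopped that early would have no Day 3 peak, which could add to the imbalance; this is not in the figures.

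**What to change.** In SAP 6.2, derive Cmax and tmax separately for Day 1 (dose 1) and Day 3 (dose 3), with tmax in hours from that day's actual dose. In SAP 6.3, summarise both by day and treatment, keeping median (min, max) for tmax, and do not pool peaks across days. SAP 5.4.5 makes its QTc predictions at the geometric means of individual Cmax values, so it should then say which Cmax it uses.

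The cost is SAP wording and an extra row per analyte in the PK tables. All samples and dosing times are already collected. One limit remains: the first post-dose sample is at 1 h, later than the cited median AQ tmax of 0.79 h, so AQ tmax stays coarse even when defined by day.

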The remaining three treatments will be re-randomised in such a way that across the whole study there will be still 12 subjects dosed with Treatment 2, 12 subjects with Treatment 3 and 12 Subjects with treatment 4. This is taking into account both the already dosed subjects with their originally randomised treatments and the newly randomised subjects yet to be included. Furthermore, within each cohort of up to eight subjects, each of the three treatments (2, 3, and 4) needs to be represented with a maximum of four and a minimum of one subject in the same cohort.

Subjects will be screened within 20 days prior to entering the study on Day -1. Each subject will receive verbal and written information followed by signing of the Informed Consent Form (ICF) prior to any screening procedures taking place. Subjects will be admitted to the study unit on Day -1 and will be discharged on Day 4.

All subjects will attend the unit for an outpatient visit on Days 8, 15, 22, 29 and a follow-up visit on Day 36 (+/- 1 day). All the assessments performed during the study are detailed in the study schedule of assessments (Table 1 and Table 2). Study design features as well as number of subjects may be adapted according to the Adaptive Features (Table 3). This study will use a sentinel dosing strategy, for full details see Section [3.3.4](#).

Number of subjects:

The planned total number of subjects for this study will be 52.

Main criteria for admission:

Black males or females, of sub-Saharan African origin (both parents are black and are of sub-Saharan African origin) will be included if they are aged between 18 and 45 years with a body mass index (BMI) between 18.0-25.0 kg/m². Subjects must agree to use effective methods of contraception.

Main exclusion criteria are: Current or recurrent disease (or condition) that could affect the action, absorption or disposition of ATV-PG or AQ, and any other significant disease or disorder which, in the opinion of the Investigator, may either put the subject at risk because of participation in the study, may influence the result of the study, or the subject's ability to participate in the study.

Anticipated test treatment(s) and mode of administration:

Oral doses of ATV-PG (1000-400 mg) and AQ (612 mg) administered once daily on Days 1 to 3 in the fed state (see Section [6.1.2](#) for details).

Reference treatment(s) and mode of administration:

Oral doses of unmatched placebo for ATV-PG and AQ.

Criteria for evaluation:

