Amodiaquine (AQ) is a synthetic 4-aminoquinoline with schizonticidal activity against *Plasmodium (P.) falciparum*, *vivax*, *ovale* and *malariae*, resulting in killing of intra-erythrocytic forms. Although the mechanism of action is not fully understood it is accepted that 4-aminoquinoline derivatives penetrate infected red blood cells and prevent the parasite from polymerizing toxic haem to insoluble haemozoin, leading to parasite death. AQ is extensively metabolised to desethyl-amodiaquine (DEAQ), the principal active component, via CYP2C8 [7]. Both AQ and DEAQ inhibit CYP2D6, although no clinically relevant pharmacokinetic interaction has been documented [7].

In healthy subjects following administration of artesunate-amodiaquine (ASAQ), the median t_{max} (range) of AQ and DEAQ respectively was 0.79 (0.48-8) hours and 2 (1.33-8) hours [10]. Following administration to patients, the mean elimination half-life of AQ was 7.9 hours and the terminal elimination half-life of DEAQ was 211 hours [11]. When ASAQ was taken with a high fat meal, the C_{max} and $AUC_{(0-t)}$ of DEAQ increased 18% and 12% respectively, compared to fasting [7].

Malarone® is a fixed-dose combination of atovaquone (ATV) and proguanil (PG) hydrochloride which is active against the erythrocytic and pre-erythrocytic (hepatic) stages of *Plasmodium* species. ATV and PG interfere with 2 different pathways involved in the biosynthesis of pyrimidines required for nucleic acid replication. ATV is a selective inhibitor of parasite mitochondrial electron transport. PG is metabolised to the active metabolite cycloguanil (CG), which inhibits dihydrofolate reductase leading to disruption of deoxythymidylate synthesis [6]. In addition, PG acts synergistically with ATV [12].

ATV is eliminated largely unchanged in the faeces, while 40% to 60% of PG is excreted by the kidneys. PG is metabolised to CG primarily via CYP2C19 [6], and to a lesser extent CYP3A4, however CYP3A4 may play a larger role in conversion of PG to CG in CYP2C19 poor metabolisers [12], and it is noteworthy that ATV is an inhibitor of CYP3A4 [12].

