Procedure	Scr D-21-D-2	D -1	D1	D2	D3	D4	D8	D15	D22	D29	Follow-up visit D36+/-1
Informed consent	X										
Demographic data	X										
Medical history and current medications	X	X ^a									
Urine drugs of abuse screen	X	X									
Breath alcohol test	X	X									
Serology HIV1&2, Hep B&C	X										
Serum pregnancy test ^b	X	X								X	X
FSH ^c	X										
Inclusion/Exclusion criteria	X	X									
Smoking history (pack/year) and current	X										
Study Residency		X	X	X	X						
Check-in		X									
Check-out						X					
Non-residential visit							X	X	X	X	X
Randomisation			X								
Study drug administration ^d			X	X	X						
Meals ^e		X	X	X	X	X					
Safety and tolerability:											
AE recording/ concomitant medication	X	X	X	X	X	X	X	X	X	X	X
Physical examination	X	X ^f			X ^f	X					
Vital signs ^g	X		X	X	X	X					X
Telemetry ^h				X		X					
24h Holter ECG ⁱ	X										
12-lead ECG in triplicate ^g	X		X	X	X	X	X	X	X		X
Body height	X										
Body weight	X										
BMI	X										
Haematology/Biochemistry/Coagulation ^l	X	X		X	X	X	X	X	X	X	X
Urinalysis	X	X								X	
Basic neurological exam			X	X	X	X	X			X	
Questionnaire Profile of Mood Scale (POM)			X			X	X			X	

Procedure	Scr D-21-D- 2	D -1	D1	D2	D3	D4	D8	D15	D22	D29	Follow- up visit D36+/-1
CYP2C8 Genotyping Sample			X ^k								
Pharmacokinetic assessments											
PK blood sampling - ATV			X	X	X	X	X	X			
PK blood sampling - PG/CG			X	X	X	X					
PK blood sampling - AQ			X	X	X	X					
PK blood sampling - DEAQ			X	X	X	X	X	X	X		

a: Update only.

b: Females of childbearing potential only.

c: A hormonal test for FSH will be done for females at screening who believe they are post-menopausal. If female subjects are confirmed as post-menopausal then these subjects will not require any further serum pregnancy tests.

d: Dosing will be carried out in the fed state. On the morning of each dosing day (Days 1, 2 and 3), a standardised meal will be served 30 mins before dosing and must be finished 10 mins before dosing, firstly with the ATV-PG / placebo tablets, followed by the AQ dispersible/ placebo tablets.

e: Standard meals will be served at standard unit times. On Days 1 to 3, the 1st meal is breakfast, lunch given 5 hours post-dose and no other meals are given before completion of the 2-4 hours post-breakfast cardiac assessments. On Day 4 (dismissal day) meals will be optional.

f: Symptom directed examination.

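### The optional 20% extrapolation limit falls near the typical DEAQ subject; if applied, it could remove a material share of DEAQ AUC0-inf values and probably bias that one summary low

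*SAP*

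**What the plan says.** SAP 6.2 defines AUC0-inf as "Area under the plasma concentration-time curve from time zero extrapolated to infinity" and lists it, with Cmax, tmax, AUC0-t, lambda_z and half-life, for each of the five analytes. It then introduces a list of conditions with "The following conditions for PK parameter inclusion may also be applied". Two of them matter here.

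- AUC0-inf "is excluded if the %extrapolated is greater than 20" percent.
- AUC, lambda_z and half-life are "to be excluded if the regression does not include at least 3 different time points in the terminal phase". The word AUC carries no subscript.

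The SAP does not say when the conditions are triggered, how many exclusions are expected, or whether a summary that includes the excluded values will be shown.

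The protocol's Introduction says that, in patients, "the terminal elimination half-life of DEAQ was 211 hours"; it gives no spread. In Protocol Table 1 (section 3.1) the row "PK blood sampling - DEAQ" is marked on Days 1-4, 8, 15 and 22, and not on Day 29 or Day 36. Doses are "administered once daily on Days 1 to 3 in the fed state".

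**The concern.** A limit on extrapolation does little harm when it catches a few poorly sampled profiles. It is different when the sampling schedule and the half-life put an ordinary subject at the limit. Inclusion then depends mainly on each subject's half-life, and the slow eliminators drop out. If slow elimination reflects low clearance, these are also the subjects with the largest AUC0-inf, so the summary is selected on the quantity it describes.

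DEAQ is the principal active component of AQ according to the protocol's Introduction. AUC0-inf is a named secondary parameter, and a secondary objective is to describe PK alone and in combination. The arms are small: 12 planned on AQ alone and 8 who received the combination (SAP 3.1). Losing several values per arm changes what the table means. Because the conditions are optional, the choice to apply them can be made after the concentrations are known.

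**Working it through.** The documents state no expected extrapolated share, so there is no planned figure to reproduce.

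**Inputs from the documents.** DEAQ half-life 211 h. Doses at 0, 24 and 48 h. Last DEAQ sample on Day 22, nominally 21 × 24 = 504 h after dose 1, 480 h after dose 2 and 456 h after dose 3. Limit 20%.

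**Assumed, because the documents do not give it.** Log-normal half-life with mean 211 h and between-subject CV of 15%, 25% or 40%; a quantifiable Day 22 sample; patient half-life applied to healthy subjects.

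**Typical subject.** k = ln 2 / 211 = 0.003285 per h. Under mono-exponential superposition the extrapolated share is the mean of exp(-504k), exp(-480k) and exp(-456k):

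(0.1910 + 0.2066 + 0.2236) / 3 = 0.207, or 20.7%.

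The SAP does not say which dose is time zero. With the clock at the third dose the share is exp(-456k) = 22.4%. The half-life at which a subject crosses 20% is 206 h (first-dose clock) or 196 h (third-dose clock).

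If a share g of the AUC lies in faster early phases, the extrapolated share becomes (1 - g) × 20.7%: 18.6% at g = 10%, 16.6% at 20% and 14.5% at 30%. If the last quantifiable sample were on Day 15, the mono-exponential share would be 36.0%.

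**Loss and bias if the rule is applied.** 400,000 simulated half-lives per setting, first-dose clock. The last two columns give the retained arithmetic mean AUC0-inf divided by the full mean. Ranges run over CV 15-40%.

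| AUC in early phases | Excluded | Half-life varies through clearance only | Half the variance is clearance |
|---|---|---|---|
| 0% | 45-53% | 0.73-0.88 | 0.86-0.94 |
| 10% | 35-38% | 0.76-0.91 | 0.88-0.96 |
| 20% | 18-30% | 0.79-0.95 | 0.90-0.98 |
| 30% | 5-22% | 0.84-0.98 | 0.92-0.99 |

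If half-life varies only through volume, the ratio is 1.00 in every row: values are lost but the mean is not biased. In the first row, 45-53% corresponds to about 5-6 of 12 subjects on AQ alone and about 4 of 8 on the combination. Reading 211 h as a median instead, with CV 20-40%, gives 52-54% excluded in the first row and 12-28% in the last.

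**Comparison analyte.** Atovaquone is sampled to Day 15. At its quoted median half-life of 87.2 h the share is 8-10%, and at the top of the quoted range (116 h) 16-18%. Both are below the limit, so this difficulty does not extend to atovaquone.

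**The three-point condition.** SAP 6.2 defines AUC0-t as the area to the last quantifiable concentration. It is a trapezoidal sum and needs no lambda_z. A failed terminal regression is therefore no reason to exclude it, yet the unqualified word AUC does so.

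**The case against.** The strongest reply is that the 20% limit is a reasonable reliability rule. After Day 4, DEAQ is sampled only on Days 8, 15 and 22, so lambda_z rests largely on three late points, and a heavily extrapolated AUC0-inf is noisy and depends on the model. The conditions are optional, the study is exploratory and descriptive, and the summaries report n, so lost values would be visible. All of this is fair. It argues for flagging such values and against presenting them without comment. It does not settle whether a summary restricted to fast eliminators should stand alone.

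Four stronger readings are tempting, and the documents do not support them.

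- **That DEAQ exposure as a whole is biased low.** The 20% rule affects AUC0-inf only. Cmax and AUC0-t are still summarised, and with a quantifiable Day 22 sample AUC0-t already is the AUC to Day 22.
- **That the QT conclusions are affected.** The SAP 5.4.5 model uses individual concentrations and predicts at geometric mean Cmax. AUC0-inf does not enter it.
- **That about half of the subjects will be dropped and the mean will be low.** Use of the rule is discretionary. The half figure needs mono-exponential decline, whereas the protocol calls 211 h a terminal half-life and takes it from patients. The bias needs half-life to vary at least partly through clearance, which the documents do not establish.
- **That the rule will hide an interaction between the arms.** The protocol's Introduction considers the potential for a PK interaction low, and no ratio or test between arms is planned.

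**Conclusion.** The point holds for DEAQ AUC0-inf, conditional on the rule being applied. The protocol's half-life and sampling schedule put a typical subject at about 15-22% extrapolated against a 20% limit. Applying the rule could remove about half of the values under mono-exponential decline, and about 5-30% with 20-30% of the AUC in early phases.

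The loss selects on slow elimination. The summarised mean is therefore likely to be low to the extent that half-life varies through clearance: under mono-exponential decline by 12-27% if entirely, by 6-14% if half, and not at all if the variation is in volume. These sizes rest on an assumed CV of 15-40% and on a half-life carried over from patients.

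Two defects need none of these assumptions: the use of an outcome-dependent exclusion is left open, and the three-point condition as worded also removes AUC0-t. The matter concerns one secondary descriptive parameter, but it is cheap to put right and should be settled before the PK data are summarised.

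**What to change.** 1. In the three-point condition of SAP 6.2, replace AUC by AUC0-inf, so that AUC0-t is kept whatever the terminal regression shows.
2. For DEAQ, state in advance that AUC0-inf is summarised for all subjects with an estimable lambda_z, with the extrapolated percentage listed and values above 20% flagged. Show the summary without the flagged values alongside, and report the number flagged in each arm.
3. Name AUC to Day 22, in all subjects, as the main DEAQ exposure summary for setting the combination beside AQ alone. It equals AUC0-t when the Day 22 sample is quantifiable. State which dose is time zero.

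The cost is SAP wording and one extra table, with no new samples or visits. The drawback is that some reported AUC0-inf values will rest on more than 20% extrapolation, which the flag makes visible.
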